Appendix 2: Guideline for Management of Neutropenia

Based on data from previous clinical studies, treatment with fostamatinib may be associated with lowering of absolute neutrophil count (ANC).

A decrease in ANC may require adjustment of the dose of study drug. Follow the dose adjustment guidelines in Table 1 and outlined below when adjusting the dose of study medication.

Table 1: Dose Adjustment

Starting Dose	Dose Level -1	Dose Level -2	Dose Level -3 ^a	Dose Level -4 ^a
100 mg PO bid	150 mg PO qd	100 mg PO qd	Discontinue	-----
150 mg PO bid	100 mg PO bid	150 mg PO qd	100 mg PO qd	Discontinue

^a The Sponsor's Medical Monitor should be consulted prior to consideration of dose modification to levels -3 or -4.

Decrease in absolute neutrophil count (ANC) to < 1,000/ μ L:

- Repeat ANC within 72 hours in the local laboratory.
- If repeat testing confirms that ANC is < 1,000/ μ L, hold study drug dosing.
 - Repeat ANC at 72 hour intervals.
- When ANC recovers to > 1,500/ μ L, restart study drug at dose level -1.

Second event of ANC < 1,000/ μ L:

- Confirm ANC as above.
- If confirmed, hold study drug until ANC > 1,500/ μ L.
- Restart study drug at dose level -2.

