7.4 Dose Adjustments Due to Adverse Events

Clinical testing to date has revealed adverse events that may require temporary interruption of the study drug and/or a reduction in study drug dose. Modification of study drug administration may be required under the following circumstances:

- Increases in ALT, AST, or bilirubin (refer to [Appendix 1](#) for guidance regarding LFT-related dose adjustments).
- ANC < 1000/mm³ or 1.0 x 10⁹/L (refer to [Appendix 2](#) for guidance regarding management of neutropenia).
- Severe diarrhoea (refer to [Appendix 3](#) for guidance regarding diarrhoea-related dose adjustments).⁽⁶⁾
- Hypertension uncontrolled by oral antihypertensive medications (refer to [Appendix 4](#) for guidance regarding hypertension-related dose adjustments).
- Other severe or life-threatening adverse events considered related to study drug administration.

Subjects who have their dose reduced will not have their dose increased for the remainder of the study. When dose interruption or reduction is required, subjects and study staff will remain blinded to the original treatment allocation; however, subjects and study staff will be aware of the switch to a reduced dose level.

Subjects for whom dose reduction results in a once daily dose of fostamatinib or matching placebo will take the daily study drug dose in the morning. Table 4 details the strategy for dose adjustment in subjects who experience AEs requiring dose reduction.

Table 4: Dose Adjustment

Starting Dose	Dose Level -1	Dose Level -2	Dose Level -3 ^a	Dose Level -4 ^a
100 mg PO bid	150 mg PO qd	100 mg PO qd	Discontinue	-----
150 mg PO bid	100 mg PO bid	150 mg PO qd	100 mg PO qd	Discontinue

^a The Sponsor's Medical Monitor should be consulted prior to consideration of dose modification to levels -3 or -4.

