8.4 Study Drug Administration

For *bid* dosing, subjects will self-administer 1 tablet twice daily by mouth: once in the morning and once in the evening. Morning and evening doses should be at least 8 hours apart and should be taken at approximately the same time each day.

For *qd* dosing, subjects will self-administer 1 tablet daily by mouth in the morning.

Tablets may be taken with or without food. Tablets should not be taken with grapefruit juice or other known CYP3A4 inhibitors (refer to [Appendix 5](#)). In the event of gastric upset, it may be useful to take tablets with food.

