- When the ALT/AST or total (and/or conjugated) bilirubin returns to $< 1.5x$ ULN, study drug may be restarted at dose level -1.

If AST or ALT $\geq 3x$ ULN or total (and/or conjugated) bilirubin $> 2x$ ULN and subject is asymptomatic:

- Complete the appropriate LFT module of the CRF with the original laboratory test result.
- Repeat LFTs, including bilirubin and ALP, within 72 hours.
- If repeat testing shows an increase in ALT/AST or total (and/or conjugated) bilirubin and the ALT/AST value exceeds $5x$ ULN, hold dosing with the study drug.
- Repeat LFTs, including bilirubin and alkaline phosphatase every 3 days/72 hours until ALT/AST is decreasing, and should be followed until transaminase returns to $< 1.5x$ ULN.
- In subjects for whom study drug is interrupted, upon return of ALT/AST or total (and/or conjugated) bilirubin to $< 1.5x$ ULN, study drug may be restarted at dose level -1.

REFERENCES

FDA Guidance for Industry (issued July 2009) 'Drug-induced liver injury: Premarketing clinical evaluation':

<http://www.fda.gov/Drugs/GuidanceComplianceRegulatoryInformation/Guidances/ucm006499.htm>

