- Consider stool sample for microbiologic evaluation and antibiotics if subject is neutropenic.
- Begin treatment with loperamide and continue treatment until the diarrhoea has resolved:
 - 4 mg loperamide initial dose.
 - 2 mg loperamide after each subsequent loose stool.
 - Not to exceed a maximum of 20 mg (10 tablets) in 24 hours.
- When diarrhoea improves to \leq Grade 1, restart study drug at dose level -1.

Management of Second Event of Grade 3 and 4 Diarrhoea

- Temporarily withhold study drug dosing.
- Initiate aggressive fluid replacement to treat potential dehydration.
- Consider stool sample for microbiologic evaluation and antibiotics if subject is neutropenic.
- Begin treatment with loperamide and to continue treatment until the diarrhoea has been resolved:
 - 4 mg loperamide initial dose.
 - 2 mg loperamide after each subsequent loose stool.
 - Not to exceed a maximum of 20 mg (10 tablets) in 24 hours.
- When diarrhoea improves to \leq Grade 1, restart study drug at dose level -2.

REFERENCES

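### Read literally, protocol Appendices 2 and 3 send a subject already at dose level -2 back up to -1 after a first event of a different toxicity, which section 7.4 forbids

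*Protocol*

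**What the plan says.** Protocol section 7.4 sets a general rule: "Subjects who have their dose reduced will not have their dose increased for the remainder of the study". It then points to the dose ladder: "Table 4 details the strategy for dose adjustment in subjects who experience AEs requiring dose reduction". The ladder has one row per starting dose, so each level is a set dose for that row:

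- Start 100 mg bid: -1 is 150 mg qd, -2 is 100 mg qd, -3 is discontinuation.
- Start 150 mg bid: -1 is 100 mg bid, -2 is 150 mg qd, -3 is 100 mg qd, -4 is discontinuation.

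The same ladder is reprinted in Appendices 1 to 4. A footnote asks for consultation with the Medical Monitor before levels -3 or -4 are considered.

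The appendices give these restart instructions:

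- **Appendix 2 (neutropenia).** After a first confirmed ANC below 1,000/µL and recovery: "restart study drug at dose level -1". After a second such event: "Restart study drug at dose level -2".
- **Appendix 3 (diarrhoea).** After a first Grade 3 or 4 event, the drug is resumed at -1. After a second: "restart study drug at dose level -2".
- **Appendix 1 (liver tests).** In both the symptomatic and the asymptomatic branch, on recovery, "study drug may be restarted at dose level -1". There is no second-event rule.
- **Appendix 4 (blood pressure).** A reduced dose by reference to the ladder, with no level named.

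**The concern.** Appendices 2 and 3 choose the restart level by whether the event is the first or second of one toxicity. They do not look at the dose the subject is taking when the event occurs. Someone brought down to -2 by one toxicity is therefore told, on a first event of another, to resume at -1, which is a higher dose. Section 7.4 says that must not happen.

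Protocol section 3.5 lists effects on blood pressure, neutrophils, the gut and liver tests as dose-dependent, so more than one in the same subject is conceivable. A site that follows the appendix as printed could raise the dose directly after a hold for toxicity. Another site applying 7.4 would not. Two subjects with the same history could be handled differently, and nothing in the protocol tells either site which text governs.

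**Working it through.** The plan states no figure to reproduce. The check converts each ladder level to mg per day and compares it with the restart levels that the appendices name.

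**Inputs.** The levels come from Table 4 in section 7.4. Tablet counts come from section 8.4: bid dosing is one tablet twice a day, and for qd dosing "subjects will self-administer 1 tablet daily by mouth in the morning". The restart levels come from Appendices 1 to 3.

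**Daily dose = tablet strength × tablets per day.**

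- 150 mg bid: 150 × 2 = 300 mg
- 100 mg bid: 100 × 2 = 200 mg
- 150 mg qd: 150 × 1 = 150 mg
- 100 mg qd: 100 × 1 = 100 mg

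**Change on restart = (restart dose − current dose) / current dose.**

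| Starting dose | Dose when event occurs | mg/day | Restart at -1 | Restart at -2 |
|---|---|---|---|---|
| 100 mg bid | starting dose | 200 | 150 (−25%) | 100 (−50%) |
| 100 mg bid | level -1 | 150 | 150 (0%) | 100 (−33%) |
| 100 mg bid | level -2 | 100 | **150 (+50%)** | 100 (0%) |
| 150 mg bid | starting dose | 300 | 200 (−33%) | 150 (−50%) |
| 150 mg bid | level -1 | 200 | 200 (0%) | 150 (−25%) |
| 150 mg bid | level -2 | 150 | **200 (+33%)** | 150 (0%) |

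The two increases are (150 − 100)/100 = 0.50 and (200 − 150)/150 = 0.33.

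**A path that reaches the conflict**, for a 150 mg bid starter:

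1. First Grade 3 or 4 diarrhoea: Appendix 3 gives -1, 200 mg/day.
2. Second Grade 3 or 4 diarrhoea: Appendix 3 gives -2, 150 mg/day.
3. First confirmed ANC below 1,000/µL, then recovery: Appendix 2 gives -1, 200 mg/day.

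Step 3 is an increase after a reduction. For a 100 mg bid starter the same three events give 150, 100 and then 150 mg/day. Two neutropenia events followed by a first Grade 3 or 4 diarrhoea event lead to the same place. With a liver event at step 3, Appendix 1 permits the increase but does not require it.

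**Does another rule catch it?** The Table 4 footnote covers only levels -3 and -4, so a restart at -1 triggers no consultation under it. Neither section 7.4 nor the appendices say which prevails.

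**The case against.** The best defence is that the no-increase sentence in 7.4 is unconditional and sits in the body of the protocol, while the appendices are titled guidelines and 7.4 cites them for guidance. A site that reads both would not raise the dose. That is a sensible reading, but it is an inference: the appendices give explicit restart levels, 7.4 sends sites to them, and precedence is not stated.

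Second, the case is probably uncommon. Under Appendices 2 and 3 alone it takes three dose-modifying events: two of one toxicity and one of another. Sections 3.5 and 3.5.3 report little or no neutropenia in ITP patients, and section 7.6.2 excludes several marrow-suppressing drugs. This stands as a limit on frequency. It does not remove the conflict, and section 7.11 carries reduced doses and the 7.4 procedures into extended treatment, so exposure need not stop at Week 24.

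Third, SAP section 7.6.1 tabulates adverse events by fostamatinib dose at onset, so events are attributed to the dose taken. That stands, and the point is therefore about trial conduct rather than a flaw in the analysis.

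A reader might also infer more than the documents support:

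- *That a same-dose restart (-1 to -1) breaches 7.4.* Section 7.4 bars increases only. What remains is that the appendices do not say whether this outcome is intended.
- *That every toxicity appendix is at fault.* Appendix 4 names no level, and Appendix 1 is permissive and counts no events.
- *That the dose could double.* Going from 100 to 200 mg/day requires a 150 mg bid starter at level -3. Appendices 1 to 3 never assign that level, and the footnote involves the Medical Monitor before it is considered.
- *That the labels might mean steps down from the current dose.* The ladder is indexed by starting dose, so the text gives no support for this.

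**Conclusion.** The protocol contradicts itself in a narrow but definite situation. For a subject already at -2, the literal first-event instruction in Appendix 2 or 3 for a different toxicity raises the daily dose by 33% (150 mg bid starters) or 50% (100 mg bid starters), against section 7.4. A single earlier reduction to -1 produces no conflict with 7.4.

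This rests on two readings: that the levels are fixed by starting dose, as the table is laid out, and that first and second events are counted within each toxicity. The second is the natural sense of Appendices 2 and 3 but is not stated as a rule. The number of subjects affected cannot be estimated from the documents and may be small among about 75. The text still needs correcting, because a printed restart instruction should not be able to override a stated safety rule.

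**What to change.** Reconcile section 7.4 and Table 4 with the restart instructions in Appendices 1, 2 and 3 for subjects who have already had a dose reduction, so that the appendix instructions and the no-increase sentence cannot conflict. The reconciled text should also make clear whether a restart at an unchanged reduced dose is intended. The rule and the levels are for the sponsor's medical team to decide.

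The cost is a wording change in four places and a memo to sites. If it is issued as a protocol amendment, section 11.2 requires ethics committee approval before it takes effect. It adds no visits, data or patients.

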Appendix 3: Guideline for Management of Diarrhoea

Diarrhoea

- Based on data from previous clinical studies, treatment with fostamatinib may be associated with diarrhoea.
- Subjects should be made aware that they may experience diarrhoea and instructed to contact the clinical site if they experience diarrhoea.
- In some circumstances it may be necessary to adjust the dose of study drug. Follow the dose adjustment guidelines in Table 1 and outlined below when adjusting the dose of study medication.

Table 1: Dose Adjustment

Starting Dose	Dose Level -1	Dose Level -2	Dose Level -3 ^a	Dose Level -4 ^a
100 mg PO bid	150 mg PO qd	100 mg PO qd	Discontinue	-----
150 mg PO bid	100 mg PO bid	150 mg PO qd	100 mg PO qd	Discontinue

^a The Sponsor's Medical Monitor should be consulted prior to consideration of dose modification to levels -3 or -4.

Grading of Severity of Diarrhoea: The US National Cancer Institute has introduced the following criteria for the grading of severity of diarrhoea: ⁽¹⁰⁾

- **Grade 1:** Increase of less than 4 stools per day over baseline
- **Grade 2:** Increase of 4 to 6 stools per day over baseline, not interfering with activities of daily living (ADL)
- **Grade 3:** Increase of ≥ 7 stools per day over baseline; incontinence; hospitalization indicated; interference with self-care ADL
- **Grade 4:** Life-threatening consequences; urgent intervention indicated
- **Grade 5:** Death

Grade 1 or 2 Diarrhoea

- Study drug may be continued.
- Discontinue all laxatives.
- Subjects should be instructed to drink 8-10 glasses of water or clear fluids per day.
- Subjects should be encouraged to make dietary changes including elimination of dairy products and eating smaller but more frequent meals.
- Consider stool sample for microbiologic evaluation and antibiotics if subject is neutropenic.

- Grade 1, consider initiating treatment with loperamide according to the regimen below (not to exceed a maximum of 20mg in 24 hours). Grade 2, initiate treatment with loperamide according to the regimen below:
 - 4 mg loperamide initial dose.
 - 2 mg loperamide after each subsequent loose stool.
- Subjects with persistent diarrhoea (> 48 hours) should be monitored carefully for dehydration and electrolyte imbalance.

Grade 3 or 4 Diarrhoea

- The subject should be instructed to withhold immediately study drug.
- Initiate aggressive fluid replacement to treat potential dehydration.
- Consider stool sample for microbiologic evaluation and antibiotics if subject is neutropenic.
- Begin treatment with loperamide and continue treatment until the diarrhoea has resolved:
 - 4 mg loperamide initial dose.
 - 2 mg loperamide after each subsequent loose stool.
 - Not to exceed a maximum of 20 mg (10 tablets) in 24 hours.
- When diarrhoea improves to \leq Grade 1, restart study drug at dose level -1.

Management of Second Event of Grade 3 and 4 Diarrhoea

- Temporarily withhold study drug dosing.
- Initiate aggressive fluid replacement to treat potential dehydration.
- Consider stool sample for microbiologic evaluation and antibiotics if subject is neutropenic.
- Begin treatment with loperamide and to continue treatment until the diarrhoea has been resolved:
 - 4 mg loperamide initial dose.
 - 2 mg loperamide after each subsequent loose stool.
 - Not to exceed a maximum of 20 mg (10 tablets) in 24 hours.
- When diarrhoea improves to \leq Grade 1, restart study drug at dose level -2.

REFERENCES

Appendix 4: Guideline for Management of Hypertension

Treatment with fostamatinib may cause blood pressure elevation in certain subjects. It is believed that this effect is a result of off-target activity against the VEGFR2 receptor. Increases in BP have proven to be amenable to treatment, generally without a requirement for study drug interruption. **Subjects with elevated blood pressure should receive prompt treatment.**

Blood pressure for all subjects should be kept below 140/90 mmHg; for subjects with increased cardiovascular risk or renal insufficiency, consideration should be given to maintaining the blood pressure below 130/80 mmHg. Subjects should remain on the same dose of ACEi or ARB during the dosing period (Visits 2-9). If additional anti-hypertensive therapy is required, other agents (beta-blockers, calcium channel blockers, or diuretics) should be added. In previous clinical studies evaluating fostamatinib, the following anti-hypertensive agents (alone or in combination) have proven effective in managing BP:

- Angiotensin converting enzyme inhibitors
- Angiotensin receptor blockers
- Calcium channel blockers
- Beta-blockers
- Diuretics

If aggressive and appropriate anti-hypertensive therapy does not control BP (< 140/90), it may be necessary to reduce the dose of study medication.

Management Algorithm for Elevated Blood Pressure

Follow the dose adjustment guidelines in Table 1 when adjusting the dose of study medication.

Table 1: Dose Adjustment

Starting Dose	Dose Level -1	Dose Level -2	Dose Level -3 ^a	Dose Level -4 ^a
100 mg PO bid	150 mg PO qd	100 mg PO qd	Discontinue	-----
150 mg PO bid	100 mg PO bid	150 mg PO qd	100 mg PO qd	Discontinue

^a The Sponsor's Medical Monitor should be consulted prior to consideration of dose modification to levels -3 or -4.

The following should result in prompt discontinuation of study medication:

- The blood pressure cannot be brought under control despite best efforts at blood pressure management.

If BP \geq 180/110 mmHg at any time after randomisation:

- Temporarily withhold dosing with study drug.
- Adjust anti-hypertensive medications.
- Reassess BP twice weekly.
- If a repeat BP \geq 180/110 mmHg despite adjusted anti-hypertensive treatment, permanently discontinue study drug.
- Increase anti-hypertensive medications until control is established.
- Restart study drug (at a reduced dose, see Table 1) when blood pressure $<$ 140/90 mm Hg.

If the BP is found to be 160-179 systolic or 100-109 diastolic at any visit after randomisation:

- Continue study drug at assigned dose level.
- Adjust anti-hypertensive therapy.
- Reassess BP twice weekly.
- If, after 1 week, the BP remains \geq 160-179 systolic or \geq 100-109 diastolic despite aggressive antihypertensive therapy, interrupt study drug administration.
- Increase anti-hypertensive medications until control is established.
- Restart study drug (at a reduced dose, see Table 1) when blood pressure $<$ 140/90 mm Hg.

If BP is \geq 140 mmHg systolic and/or \geq 90 mmHg diastolic but below 160 systolic or 100 diastolic at any visit after randomisation:

- Continue study drug at assigned dose level.
- Repeat blood pressure assessment within 1 week.
- If blood pressure remains above \geq 140 mmHg systolic and/or \geq 90 mmHg diastolic after 1 week adjust antihypertensive therapy.
- Continue to monitor BP weekly until control is established.
- If BP remains \geq 140 mmHg systolic and/or \geq 90 mmHg diastolic for more than 8 weeks, despite aggressive antihypertensive therapy, reduce dose of study drug (see Table 1).

REFERENCES

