3.3.2 Multiple-dose Pharmacokinetics

A 2- to 2.5-fold increase in R406 exposure (AUC) was seen at 160 mg *bid*, when Day 7 exposure was compared with Day 1. At 250 mg *bid*, a 3.3-fold increase in R406 AUC was observed on Days 7 and 20 over Day 1. The higher than unity accumulation ratio is, to a large extent, due to *bid* dosing for a compound with a relatively long half-life. A 3-fold increase in dose (from 100 to 300 mg *bid*) resulted in approximately 4-fold increase in steady-state exposure. Platelet aggregation studies were performed in the single and multiple dose PK studies; no effect on collagen or ADP-induced platelet aggregation at the highest doses tested were observed.

In Japanese healthy subjects, steady-state AUC and C_{max} were approximately dose-proportional between subjects administered 50 mg and 100 mg twice daily, and more than dose-proportional between 100 mg and 200 mg twice daily based on comparison of data across Japanese and Western studies. R406 exposure was similar in Western and Japanese subjects with considerable overlap in exposure between groups.

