3.3.5 Drug-Drug Interactions

3.3.5.1 Effect of Other Drugs on R406 Exposure

- A strong CYP3A4 inhibitor, ketoconazole, produced ~2-fold increase in exposure to R406, while a moderate inhibitor, verapamil, caused ~1.4-fold increase in R406 exposure. The magnitude of these interactions suggests that fostamatinib is not a sensitive CYP3A4 substrate and that there are alternate *in vivo* pathways of R406 metabolism in humans.
- A strong inducer of multiple CYP enzymes, rifampicin, decreased exposure to R406 to about 25% of that observed when fostamatinib is administered alone.
- Ranitidine, which increases gastric pH, did not have a clinically relevant effect on the PK of R406.
- Single dose of rosuvastatin and simvastatin did not have a clinically relevant effect on the PK of R406.

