3.5 Safety

Phase 2 and 3 studies of fostamatinib have been conducted in several indications including ITP, RA and B- and T-cell lymphomas. Doses of fostamatinib have ranged from 50 to 250 mg PO *bid*, depending on the indication being treated. The majority of patients have been treated at doses ranging from 50-150 mg PO *bid*.

The overall pattern of adverse effects of fostamatinib in these various clinical settings (patients with RA, severely ill patients with lymphoma and advanced solid tumours, chronically ill patients with ITP, and in healthy subjects), has been consistent, and includes dose-dependent effects on BP, neutrophil counts, dizziness, GI complaints and liver function test abnormalities, all of which are reversible and manageable with appropriate safety monitoring. The ITP patients (on no anti-metabolites or chemotherapy) have not manifested neutropenia, despite receiving higher doses of fostamatinib than the RA patients. The lymphoma patients have experienced more cytopenias, and infections, consistent with their extensive pre-treatment and underlying disease. In patients with solid tumours, the overall pattern of reported AEs was consistent with a population of heavily pretreated, relapsed patients with solid tumours of varying histologies.

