7.6.3 Restricted Medications Unrelated to IgA Nephropathy

Due to the potential for drug-drug interactions with fostamatinib, specific treatments are either not allowed or are restricted during the course of this study (see [Appendix 5](#)).

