Appendix 5: Restricted Medications

Subjects taking fostamatinib may be affected by drug-drug interactions.

Fostamatinib is metabolized by CYP3A4. In the presence of a strong inhibitor of CYP3A4, the systemic exposure of the active metabolite of fostamatinib may be increased significantly. **Strong inhibitors of CYP3A should not be co-administered with fostamatinib.** Inducers of CYP3A4 may lower concentrations of active drug, possibly to sub-therapeutic concentrations, and their use in subjects taking fostamatinib should be limited.

Fostamatinib is an *in vitro* inhibitor of P-glycoprotein and affects digoxin bioavailability by inhibiting P-gp. If a subject requires digoxin or is taking digoxin concurrently with fostamatinib, digoxin levels should be monitored carefully according to local practice, as the digoxin dose may need to be lowered.

Fostamatinib is known to increase the plasma concentration of the HMG-CoA reductase inhibitors simvastatin and rosuvastatin by 50-100%. If a subject develops muscle pain or weakness, the dose of HMG-CoA reductase may need to be lowered and the subject monitored closely for any adverse effects associated with myositis.

Subjects' concomitant medications should be examined for additional possible drug-drug interactions.

List of Inhibitors and Inducers of CYP3A4

The list below is not an exhaustive list (the Sponsor's Medical Monitor should be consulted in the event of questions).

Strong Inhibitors of CYP3A4

Clarithromycin	Telithromycin	Ketoconazole
Itraconazole	Fluvoxamine	Nefazodone
Ritonavir	Indinavir	Nelfinavir
Sequinavir	Atazanavir	

Moderate Inhibitors of CYP3A

Amiodarone	Aprepitant	Erythromycin
Troleandomycin	Fluconazole	Imatinib
Verapamil	Diltiazem	Amprenavir
Fosamprenavir	Grapefruit juice	Seville oranges
Star fruit		

CYP3A Inducers

Barbiturates

Pioglitazone

Carbamazepine

St. John's Wort

Efavirenz

Rifampin

Phenytoin

Nevaripine

Rifabutin

Modafinil

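### Section 8.4 bars known CYP3A4 inhibitors, but Appendix 5 gives no rule for moderate ones, and the blood pressure guidance offers calcium channel blockers without excluding verapamil or diltiazem

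*Protocol*

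**What the plan says.** Three parts of the protocol bear on whether a subject may take verapamil or diltiazem with study drug.

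- **Administration rule.** Section 8.4: "Tablets should not be taken with grapefruit juice or other known CYP3A4 inhibitors", with a reference to Appendix 5. No strength of inhibition is specified.
- **Restricted medications.** Section 7.6.3 says "specific treatments are either not allowed or are restricted during the course of this study" and leaves the detail to Appendix 5. Appendix 5 states "Strong inhibitors of CYP3A should not be co-administered with fostamatinib". It asks that CYP3A4 inducers be limited and gives advice for digoxin and two statins. Its moderate-inhibitor list includes verapamil, diltiazem and grapefruit juice, with no instruction attached. It also asks for a general check of concomitant drugs for interactions and names the Medical Monitor as contact for questions.
- **Blood pressure guidance.** Appendix 4 and Section 7.6.1 hold the ACEi or ARB dose fixed over Visits 2-9 and say that "other agents (beta-blockers, calcium channel blockers, or diuretics) should be added" if more is needed. Inclusion criterion 8 (Section 6.1 and the synopsis) permits the same three classes. None of these places excludes the two drugs or refers to Appendix 5.

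On size, Section 3.3.5.1 reports that "a moderate inhibitor, verapamil, caused ~1.4-fold increase in R406 exposure". Table 4 sets the first reduction from 150 mg bid at 100 mg bid.

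SAP Section 7.2 will count subjects who change anti-hypertensive regimen. Its list of drug classes includes diuretics and beta blockers but not calcium channel blockers.

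**The concern.** A site that follows Section 8.4 would avoid verapamil and diltiazem. A site managing a pressure rise from Appendix 4, with Appendix 5 at hand, finds the drug class recommended and no ban on these two members. Blood pressure elevation is a known dose-dependent effect of fostamatinib, so the add-on drug could raise exposure to the likely cause of the problem being treated.

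When pressure stays high, Appendix 4 reduces the study drug dose. If verapamil arrives at about the same time, much of the intended fall in exposure may not occur. Section 7.4 adds that "Subjects who have their dose reduced will not have their dose increased for the remainder of the study", so a reduction for toxicity that arose on verapamil would remain after verapamil was replaced. That sequence is possible but cannot be quantified.

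The SAP gap is related: a calcium channel blocker added during treatment would not be counted as a regimen change, although the protocol recommends the class.

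**Working it through.** **Does Section 8.4 reach moderate inhibitors?** Yes, on its wording. It covers known CYP3A4 inhibitors in general, and the one item it names, grapefruit juice, is on Appendix 5's moderate list. It cannot be read as meaning strong inhibitors only.

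**Inputs for the size of the effect**

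- Verapamil multiplies R406 exposure by v, about 1.4 (Section 3.3.5.1). No interval is given, so 1.3 to 1.5 is used here as an assumed range.
- First reduction: 150 mg bid to 100 mg bid (Table 4).
- Dose and exposure: roughly proportional for single doses of 100 to 300 mg (Section 3.3.1). At steady state, going from 100 to 300 mg bid "resulted in approximately 4-fold increase in steady-state exposure" (Section 3.3.2).

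The protocol states no offset figure to reproduce.

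**Formulas.** Let r be exposure at 100 mg bid divided by exposure at 150 mg bid.

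- Proportional: r = 100/150 = 0.667.
- Power model from the steady-state statement: exponent ln 4 / ln 3 = 1.262, so r = (100/150)^1.262 = 0.600.
- Straight line through the same two steady-state points: exposure at 150 mg is 1 + 3 × (50/200) = 1.75 times that at 100 mg, so r = 1/1.75 = 0.571.

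If verapamil is absent before the reduction and present after it, the share of the intended fall that is offset is (v·r − r)/(1 − r).

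| Exposure model | Intended fall | Level with v = 1.4, relative to 150 mg bid alone | Offset, v = 1.3 | Offset, v = 1.4 | Offset, v = 1.5 |
|---|---|---|---|---|---|
| Proportional | 33% | 93% | 60% | 80% | 100% |
| Power 1.262 | 40% | 84% | 45% | 60% | 75% |
| Straight line | 43% | 80% | 40% | 53% | 67% |

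**If verapamil is already in use**, exposure goes from v to v·r. The ratio is r, so the reduction has its full relative size (33-40% under the first two models) and nothing is offset.

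**Which timing applies?** In Appendix 4's branch for pressures of at least 140/90 but below 160/100, therapy is adjusted first and the dose is reduced only after more than 8 weeks. Verapamil would usually be in place by then. In the branch at or above 180/110, study drug is withheld while anti-hypertensives are adjusted, then restarted at a reduced dose. In the 160-179/100-109 branch, an interruption may follow after a week, with further increases in therapy. The offset can arise in these two branches.

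**Other points of scale**

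- 150 mg bid with verapamil resembles 150 × 1.4 = 210 mg bid (proportional) or 150 × 1.4^(1/1.262) = 196 mg bid (power). That is above this trial's doses but within the 50-250 mg bid range reported in Section 3.5.
- From 100 mg bid, the first step is 150 mg qd, a daily dose of 200 mg falling to 150 mg. If daily exposure follows daily dose, r is 0.75 or 0.75^1.262 = 0.696. Times 1.4, this gives 105% or 97% of the starting exposure. With the 100 mg cohort through Week 26 (Section 10.9), this step now matters only in extended treatment.
- The documents give no figure for diltiazem.

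**The case against.** The strongest reply is that the protocol already answers the question. Section 8.4 is explicit and sends the reader to a list that names both drugs. Appendix 5 does not permit moderate inhibitors; it is silent on them, asks for an interaction check and gives a contact. On this view there is a clarity gap, not two opposite orders. That is a fair description. It does not remove the gap: Section 7.6.3 relies on Appendix 5 to say what is restricted, and the Medical Monitor is consulted only when someone has a question, which Appendix 4 does not prompt.

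A second reply is that the interaction is modest. Section 3.3.5.1 concludes that fostamatinib is not a sensitive CYP3A4 substrate, and Section 3.5 calls the dose-dependent effects "all of which are reversible and manageable with appropriate safety monitoring". A ban on strong inhibitors alone would fit that view, and narrowing Section 8.4 would also make the texts agree. This limits the severity. But that edit would leave the blood pressure guidance offering a drug that raises exposure to the likely cause of the rise.

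A reader might also infer that only the blood pressure rechecks would catch a problem after dosing. The protocol does not support that. Haematology, serum chemistry, adverse events and concomitant medications are reviewed at every treatment visit after baseline. Appendices 1-3 have their own triggers for holding or reducing the dose, and the Safety Review Committee monitors throughout.

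**Conclusion.** The inconsistency stands as a minor safety and consistency point. It affects Cohort 2 and extended treatment, including placebo subjects who move to 150 mg bid under Section 7.11.1.

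The offset of roughly 60-80% is conditional. It assumes that verapamil is first added around the reduction from 150 to 100 mg bid, that the ratio is 1.4, and that exposure follows the proportional or power model. Straight-line interpolation gives 53%. Ratios of 1.3 to 1.5 widen the range to about 45-100% under the proportional and power models. A reader might take 60-80% as a general loss of effect of dose reduction; it is not, because a subject already on verapamil gets the full relative reduction.

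A reader might also infer that verapamil would narrow the exposure difference between the dose groups. The documents do not support this. With the 100 mg cohort through Week 26, main-study use now falls on 150 mg subjects, and in those not reduced it would widen the difference.

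How often either drug would be chosen, and any clinical harm, cannot be derived. No effect on the primary analysis is shown.

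**What to change.** 1. In Appendix 5, state that moderate CYP3A inhibitors should also be avoided with study drug, in line with Section 8.4.
2. In Appendix 4, Section 7.6.1 and inclusion criterion 8 (with its synopsis copy), write *calcium channel blockers other than verapamil or diltiazem (see Appendix 5)*.
3. In SAP Section 7.2, add the calcium channel blocker class to the anti-hypertensive list, so that adding one counts as a regimen change.

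The cost is a few lines of protocol wording and one line in the SAP. The downside is a slightly narrower choice of add-on drug, and a subject already on verapamil or diltiazem must switch. Beta-blockers, diuretics and other calcium channel blockers remain available.
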